7.1.1 Temporary Discontinuation

Dose interruption requiring rescheduling of IP administration outside the visit window indicated in the SoA (Table 1) should be an exception and the reason should be recorded in the eCRF. Dose delays longer than 10 days may only happen upon approval of the AstraZeneca Study Physician and at the discretion of the Study Physician, and if not authorized will be considered a discontinuation of study intervention. Procedures for E/D follow-up should be followed as specified in the SoA (Table 1). Study treatment may be temporarily discontinued for reasons such as the following:

- Adverse event
- Unforeseen circumstances resulting in delayed visit (ie, illness, or personal events)

7.2 **Participant Withdrawal from the Study**

A participant may withdraw from the study at any time at his/her own request, or may be withdrawn at any time at the discretion of the investigator for safety, behavioral, compliance, or administrative reasons. This is expected to be uncommon.

A participant who considers withdrawing from the study must be informed by the investigator about modified follow-up options (e.g., telephone contact, a contact with a relative or treating physician, or information from medical records).

At the time of withdrawal from the study, if possible, an Early Study Intervention Discontinuation visit should be conducted, as shown in the SoA. See SoA for data to be collected at the time of study withdrawal and follow-up and for any further evaluations that need to be completed. Then the participant will discontinue the study intervention and be withdrawn from the study at that.

A participant who withdraws consent will always be asked about the reason(s) and the presence of any AE and history of asthma exacerbation. The Investigator will follow up participants as medically indicated. A withdrawal visit is essential to collect as much safety data, as possible for the participant as per E/D described in the SoA (Table 1).

If the participant withdraws consent for disclosure of future information, the sponsor may retain and continue to use any data collected before such a withdrawal of consent.

If participant chooses to withdraw from the study and as a result discontinues from the study intervention, if possible, an E/D follow-up should be conducted, as shown in the SoA (see Section 7.2 for further details). It should be confirmed if he/she still agrees for existing samples to be used in line with the original consent.

If he/she requests withdrawal of consent for use of samples, destruction of any samples taken and not tested should be carried out in line with what was stated in the informed consent and local regulation The investigator must document the decision on use of existing samples in the site study records and inform the Study Team.

7.3 Lost to Follow-up

A participant will be considered lost to follow-up if he or she repeatedly fails to return for scheduled visits and is unable to be contacted by the study site.

The following actions must be taken if a participant fails to return to the clinic for a required study visit:

- The site must attempt to contact the participant and reschedule the missed visit as soon as possible and counsel the participant on the importance of maintaining the assigned visit schedule and ascertain whether or not the participant wishes to and/or should continue in the study.
- Before a participant is deemed lost to follow up, the investigator or designee must make every effort to regain contact with the participant (where possible, 3 telephone calls and, if necessary, a certified letter to the participant's last known mailing address or local equivalent methods). These contact attempts should be documented in the participant's medical record.

Should the participant continue to be unreachable, he/she will be considered to have withdrawn from the study.

Site personnel, or an independent third party, will attempt to collect the vital status of the participant within legal and ethical boundaries for all participants enrolled, including those who did not get investigational product. Public sources may be searched for vital status information. If vital status is determined as deceased, this will be documented, and the participant will not be considered lost to follow-up. Sponsor personnel will not be involved in any attempts to collect vital status information.

Discontinuation of specific sites or of the study as a whole are handled as part of Appendix C.

8 STUDY ASSESSMENTS AND PROCEDURES

Study procedures and their timing are summarized in the SoA (Table 1). Protocol waivers or exemptions are not allowed.

The Investigator will ensure that data are recorded in the eCRFs. An electronic system will be used for data collection and query handling. The Investigator will also ensure the accuracy, completeness, legibility, and timeliness of the data recorded and of the provision of answers to data queries according to the Clinical Study Agreement. The Investigator will sign the completed eCRFs. A copy of the completed eCRFs will be archived at the study site. In case of civil crisis, natural disaster, or public health crisis, additional data to assess the impact of such events will be collected.

Immediate safety concerns should be discussed with the sponsor immediately upon occurrence or awareness to determine if the participant should continue or discontinue study intervention.

Adherence to the study design requirements, including those specified in the SoA, is essential and required for study conduct.

All screening evaluations must be completed and reviewed to confirm that potential participants meet all eligibility criteria. The investigator will maintain a screening log to record details of all participants screened and to confirm eligibility or record reasons for screening failure, as applicable.

Procedures conducted as part of the participant's routine clinical management (e.g., blood count) and obtained before signing of the ICF may be utilized for screening or baseline purposes provided the procedures met the protocol-specified criteria and were performed within the time frame defined in the SoA.

The average amount of blood collected from each participant over the duration of the study, including any extra assessments that may be required, will be approximately 30 mL (depending on the local laboratory sample processing procedure) and will not exceed 50 mL. Repeat or unscheduled samples may be taken for safety reasons or for technical issues with the samples.

8.1 Efficacy Assessments

8.1.1 Functional Respiratory Imaging (FRI)

Functional Respiratory Imaging (FRI) is a quantitative method to measure biological responses to therapeutic interventions through structural and functional parameters using high-resolution CT and computational fluid dynamics. All CT scanners used in this study must be at least a 64-slice scanner. For a helical scan, the scanner should be able to acquire at least 64 slices per rotation using a slice thickness of 0.625 mm or lower (collimation of

64 x 0.625 mm, 128 x 0.5 mm, 256 x 0.6 mm, etc.) using a tube voltage of 100kV. FRI analyses will be conducted by a central vendor who will provide further guidance on the CT scanner requirements, CT scan procedure and scanner-specific scanning protocol settings required for the current study in a separate manual and guidance document. Study team training will also be provided by the central vendor to all relevant study team members prior to study center activation. Clinical evaluation of CT scans should be done by the study team as per local practice, and any abnormality identified should be recorded as an AE in the eCRF.

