In addition to bronchoconstriction and airway thickening, mucus plugging is common and often persistent in patients with asthma and seen on CT scans of most patients. Eosinophils are the major cell type found in the Charcot-Leyden crystals in mucus plugs of asthmatics. Mucus plugs with eosinophilic inflammation may have a profound effect on pulmonary function and the development of exacerbations, and imaging of bronchial segments and scoring of mucus plugging is a well-accepted research tool in respiratory disease (Oguma et al., 2021).

Depletion of eosinophils should lead to a reduction in mucus plugging on imaging and improvement of airway patency and airflow distribution. Kooner et al. demonstrated that patients with high baseline mucus score had significant improvements in VDP and asthma control post-benralizumab while participants with low mucus score did not (Kooner et al., 2021).

Ongoing trials like the CHINOOK study will also evaluate the relationship between any observed effects on airway remodeling, improvements in lung physiology and airway dynamics in response to benralizumab; however, this study is primarily focused on the impact on airway remodeling by morphological and histological measures in subjects with severe eosinophilic asthma (NCT03953300; ClinicalTrials.Gov).

This mechanistic study will thus investigate the short-term benefits of sustained depletion of airway eosinophils by benralizumab on airway dynamics and mucus plugs in participants with

severe eosinophilic asthma. The relationships between airway dynamic measurements and

parameters measured at baseline and following treatment with benralizumab.

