The clinical benefit demonstrated in clinical trials, combined with the overall safety profile of benralizumab has established a positive benefit-risk profile for the approved severe asthma indication. Risk minimization measures include the exclusion of participants with allergy or reaction to any component of the benralizumab formulation, untreated helminth parasitic infection and active or recent malignancy, while concurrently performing routine pharmacovigilance activities.

Risks of the study design are those associated with computed tomography (CT). In clinical practice, patients with asthma are not subjected to many high-resolution CT scans. As such, undergoing the CT procedure during this study may result in a benign or incidental finding. The use of CT also involves ionizing radiation that increases the risk of radiogenic tumors in participants and may also pose a risk to embryo fetal development and infant. Steps will be taken to minimize these risks including the exclusion of pregnant and lactating women in the study. Further information on the steps taken to reduce radiation exposure are detailed below. The CT procedures incorporated into this study design are aligned with the directives presented in the European Union (EU) guidance (Directorate-General – Environment, nuclear safety and civil protection, 1998a). Participants will be informed of the risks associated with the CT procedure before entering the study.

In this study, extra attention will be paid to reduce radiation by providing low radiation scanning protocols tailored to the specific scanner available at participating sites. Low radiation scanning protocol guidance will be provided to sites before any subject scan visits. Participating study centers will be required to set up a study-allocated CT scanner with a low radiation scanning protocol and conduct a phantom scan using this protocol. The phantom scan will be sent to a central vendor supporting this study for FRI analysis for review and confirmation for the low radiation CT scanner settings. All study team personnel involved in the CT scanning procedure will also undergo training to ensure quality and consistency of the high-resolution CT scans are maintained across study centers. Study centers will only be certified for the CT scanning procedure after the phantom scan is approved by the central vendor and all relevant study team personnel have successfully completed their training.

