6.2 Preparation/Handling/Storage/Accountability

- 1) The investigator or designee must confirm appropriate temperature conditions have been maintained during transit for all study intervention received and any discrepancies are reported and resolved before use of the study intervention.
- 2) Only participants enrolled in the study may receive study intervention and only authorized site staff may supply or administer study intervention. All study intervention must be stored in a secure, environmentally controlled, and monitored (manual or automated) area in accordance with the labelled storage conditions with access limited to the investigator and authorized site staff.
- 3) The investigator, institution, or the head of the medical institution (where applicable) is responsible for study intervention accountability, reconciliation, and record maintenance (i.e., receipt, reconciliation, and final disposition records).
- 4) Further guidance and information for the final disposition of unused study interventions are provided in the Pharmacy Manual.

The IP will be administered at the study site on Visit 1, 2 and 3. IP will be supplied to the site in a kit with a single-use pre-filled syringe of benralizumab. Dosing should be performed following the completion of all visit assessments for Visit 1, 2 and 3.

All shipments of IP include a data logger which will allow the Investigator or designee to confirm appropriate temperature conditions have been maintained during transit for all study treatment received and any discrepancies are reported and resolved before the use of the study treatment. Only participants enrolled in the study may receive study treatment and only authorized site staff may supply the study treatment.

Only authorized site staff may administer the study treatment.

Before investigational product administration

Prior to each IP administration:

- 1) The Investigator/authorized delegate will assess the injection site as per the standards of medical care.
- 2) For WOCBP, a urine pregnancy test will be performed; IP will be administered only if the result of the test is negative.

Investigational product administration

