8.1.1.1 FRI parameters

Image acquisition

In this study, the FRI parameters will be obtained through first the acquisition of low dose, high-resolution computed tomography (CT) thorax scans of participants in the study using a low radiation scanning protocol installed on a study-allocated CT scanner before study initiation at the study center.

All participants in the study will undergo two high-resolution scans, one each at Total Lung Capacity (TLC) and Functional Residual Capacity (FRC) with gating, at both Visits 1 and 4 as specified in the SoA (Table 1). All CT scans will be conducted with respiratory gating using equipment (CE-marked) provided by the central vendor. All CT scan procedures should also be conducted before spirometry testing (see Section 8.1.2 for further details).

Participants should withhold their usual maintenance and rescue therapies **before Visit 1 and Visit 4** where CT procedures will be scheduled as below:

- Short-acting muscarinic antagonists (SAMAs) or CCI /SAMA combinations should be withheld at least 12 hours prior to Visit 1 and Visit 4 at the site.
- Twice daily LABA-containing therapies should be withheld for at least 12 hours prior to Visit 1 and Visit 4 at the site.
- Once daily LABA-containing therapies should be withheld for at least 24 hours prior to Visit 1 and Visit 4 at the site.
- Once daily LAMA-containing therapies should be withheld for at least 24 hours prior to Visit 1 and Visit 4 at the site.
- Twice daily LAMA-containing therapies should be withheld for at least 12 hours prior to Visit 1 and Visit 4 at the site.

- LTRA should be restricted for at least 24 hours prior to Visit 1 and Visit 4 at the site.
- Twice daily theophyllines should be withheld for at least 12 hours prior to Visit 1 and Visit 4 at the site.
- Once daily theophyllines for at least 24 hours prior to Visit 1 and Visit 4 at the site.

Image processing

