8.4.1 Time Period and Frequency for Collecting AE and SAE Information

Adverse events will be collected from after the participant received the first dose of the study intervention, throughout the treatment period and including the follow-up period (Visit 5, last contact), or up until follow-up for early discontinuation.

SAEs will be recorded from the time of signing of the informed consent form.

If the investigator becomes aware of a serious adverse event with a suspected causal relationship to the investigational medicinal product that occurs after the end of the clinical study in a participant treated by him or her, the investigator shall, without undue delay, report the serious adverse event to the sponsor.

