8.4.6 Disease Under Study

Symptoms of disease under study (DUS) are those which might be expected to occur as a direct result of usual, intermittent variations in disease status or response to environmental stimuli (e.g., allergens or weather) or routine pulmonary procedures (e.g., spirometry). Events which are unequivocally due to disease under study should not be reported as an AE during the study unless they meet SAE criteria or lead to discontinuation of the investigational product, or is a sign or symptom that is new to the participant or inconsistent with the participant's pre-existing asthma history as judged by the Investigator.

Asthma exacerbation should be recorded as an AE only if it fulfils any of the criteria for SAE (see Section 8.4.7) or if the AE leads to IP discontinuation.

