3.6.2 Adverse Events

3.6.2.1 Definitions and Derivations

AEs are collected from the time of first dose of IP, throughout the treatment period and until Week 15 safety follow-up period is completed. AE causality is as determined by the reporting investigator. AEs with date of onset on or after the earliest first dose of any of the components of the combination should be considered to be treatment emergent.

AEs will be coded using the most recent version of MedDRA that will have been released for execution by the Sponsor/designee.

Multiple occurrences of an AE in the same participant will only be counted once overall considering start date as the first day of first occurrence and stop date the last day of the last occurrence.

In the case that, during the study, a participant has more than one episode of the same preferred term with different levels of intensity, then the maximum intensity level will be used. The following ordering will be used to define maximum intensity level: Mild < Moderate < Severe.

For each participant and each AE, the worst severity recorded will be attributed and used in the by-severity summaries. Similarly, the worst causality (most related to study intervention) will be attributed and used in the by-causality summaries. If severity or causality is missing, a conservative approach for AE assessment (taking into account the worst case) will be followed.

Any AEs with incomplete start and end dates/times will be treated as follows:

- AEs with unknown start times, but with start date known, will be imputed with a time of 00:00, unless the start date corresponds to any given dosing date. In this case the start time will be imputed with the time of dosing. If this results in a start date/time after end date/time of the AE, then the time will also be imputed with 00:00.
- AEs with completely unknown start dates will be imputed with the date and time of dosing unless the end date is known and prior to dosing; in that case the start date will be imputed as the date of screening and a time of 00:00.
- AEs with partially known start dates/times will be treated as follows:

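### Findings on the pre-dose Visit 1 CT scan can be recorded as AEs and classed as treatment-emergent, because Protocol 8.1.1 conflicts with 8.4.1 and 8.4.6 and the SAP cannot tell pre-dose from post-dose on that day

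*Protocol*

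**What the plan says.** Protocol 8.1.1 asks the study team to evaluate the CT scans clinically under local practice, and adds that "any abnormality identified should be recorded as an AE in the eCRF". Scans are scheduled at Visits 1 and 4 (8.1.1.1 and Table 1). On order within the visit, Protocol 6.2 says "Dosing should be performed following the completion of all visit assessments for Visit 1, 2 and 3". Protocol 2.3.1 anticipates that "undergoing the CT procedure during this study may result in a benign or incidental finding".

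Two other protocol sections govern what counts as an AE:

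- 8.4.1: "Adverse events will be collected from after the participant received the first dose of the study intervention". Only SAEs are recorded from consent.
- 8.4.6: "Events which are unequivocally due to disease under study should not be reported as an AE during the study", apart from events that are serious, that lead to stopping the product, or that are signs or symptoms new to the participant or out of keeping with the asthma history.

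Protocol 8.4.2 lists start and stop dates among the AE variables, and no clock time.

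SAP 3.6.2.1 treats an AE as treatment-emergent when its onset date is on or after the first dose. For an AE with a known date but unknown time that falls on a dosing date, it says: "In this case the start time will be imputed with the time of dosing". SAP 3.6.2.2 restricts two groups to the listings, outside the AE summary tables: AEs before the first dose, and those unresolved at the participant's last assessment. The SAP Addendum does not change any of these AE rules.

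**The concern.** A finding on a scan taken before any exposure cannot be an effect of the drug. Protocol 8.1.1 nevertheless directs it to the AE form, and the SAP's date-based rule then labels it on-treatment. Protocol 8.4.5 shows that the authors knew the usual safeguard: a physical examination finding is an AE only if it is clinically relevant and new or aggravated against baseline. Section 8.1.1 has no such test for CT.

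The protocol also names no other place for these findings. Table 1 schedules medical history only at Visit 0, before any study CT.

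Safety and tolerability is a stated objective, with AEs listed first among its measures. With one arm, no comparator would show that part of the AE count comes from recording baseline scans. Two sites could also act in opposite ways, one following 8.1.1 and the other 8.4.1 or 8.4.6, and both could claim to follow the protocol.

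**Working it through.** The plan states no figure on this point, so the check traces the rules for one finding on the Visit 1 scan.

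1. **Is it recorded?** Under 8.1.1, yes. Under 8.4.1, a non-serious finding identified before the first dose is not. If it is unequivocally due to asthma, 8.4.6 also says no, subject to its exceptions. No order of precedence is given.
2. **What onset does it carry?** If dated to Visit 1, it carries the date of the first dose, because scan and dose belong to the same visit. Protocol 8.4.2 lists no time.
3. **Is it treatment-emergent?** The onset date equals the first-dose date, so SAP 3.6.2.1 says yes. The unknown time is set to the dosing time. A completely unknown start date leads to the same place: it is imputed to dosing unless the event is known to have ended earlier.
4. **Does the pre-dose exclusion in SAP 3.6.2.2 remove it?** No. The derived onset is at dosing, not before it. The exclusion would work only if a pre-dose time or an earlier date had been entered.
5. **Does the unresolved exclusion in SAP 3.6.2.2 remove it?** Read literally, yes, if the finding is still present at the last assessment. If it has cleared, no.
6. **Is it counted again at Visit 4?** No. SAP 3.6.2.1 counts repeated occurrences of an AE in one participant once.

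For a Visit 1 finding recorded under 8.1.1 with that date and no time:

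| Status at last assessment | Class | Where it appears |
|---|---|---|
| Cleared | Treatment-emergent | Summary tables and listings |
| Still present | Treatment-emergent | Listings only (literal reading) |

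The second column is wrong for a pre-dose finding in both rows, and the third depends on whether the finding went away. If a site also recorded mucus plugs under 8.1.1 despite 8.4.6, a plug that cleared on treatment, which is the hoped-for effect, could be tabulated as an on-drug AE.

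**Weight of one case.** The safety-set size is not stated. Under the planned numbers it lies between 34 (evaluable, all with three doses) and 38 (enrolled). One misclassified participant then moves an AE percentage by 1/38 = 2.6 to 1/34 = 2.9 percentage points. How many such cases to expect cannot be worked out, because the documents give no rate for incidental CT findings.

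Addendum 2.1 redefines baseline as the last measurement on or before the first dosing day. The same scan can therefore be baseline for efficacy while its findings are on-treatment for safety.

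**The case against.** The best defence is that other rules already contain the problem, and much of it stands.

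- **SAP 3.6.2.2.** A lasting lung nodule is typically unresolved at the last assessment and so, read literally, never reaches the summary tables. This stands. But it works by resolution status, not by whether the finding preceded the dose, and it leaves the classification wrong.
- **Protocol 8.4.6.** A reader might infer that baseline asthma in general becomes on-drug AEs. The documents do not support that. Section 8.4.6 exempts events unequivocally due to the disease, and Protocol 2.1 treats plugging as part of it: "mucus plugging is common and often persistent in patients with asthma and seen on CT scans of most patients". For asthma findings there is a conflict between sections, not a settled outcome. What remains is chiefly incidental findings unrelated to asthma.
- **Double counting.** A reader might infer that an unchanged abnormality counts at both visits. The once-only rule in SAP 3.6.2.1 prevents this.
- **Strength of wording.** Section 8.1.1 says should, not must, and the eCRF completion instructions, which might settle the matter, are not among the documents.
- **Causality and scope.** Causality is collected for each AE and tabulated separately, so an incidental finding can be marked unrelated. Safety output is descriptive. Both points hold and limit the harm, but the overall AE count would still include the finding.

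**Conclusion.** The AE rules for CT findings are wrong as written, in a narrow sense. Section 8.1.1 conflicts with 8.4.1 and, for asthma-related findings, with 8.4.6. Because only dates are collected, the SAP cannot separate a pre-dose Visit 1 CT finding from a post-dose event dated the same day. Pre-existing findings can therefore be counted as on-drug AEs, and whether they reach the summary tables depends on whether they clear.

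This assumes that the site follows 8.1.1, dates the finding to Visit 1 (or leaves the start date unknown) and enters no time, and that the scan precedes the dose as planned.

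The size is unknown. A reader might turn to the plug frequencies in Protocol 4.2, which are 19% and 67% with plugs in four or more segments for FEV1 of 60-80% and below 60% of predicted. Applied to 38 participants, these give 0.19 × 38 = 7.2 and 0.67 × 38 = 25.5. Those figures do not measure this problem. They assume that 8.1.1 overrides 8.4.6, they come from research plug scoring and not a local clinical read, they use everyone who consents and not those dosed, and they count recordable findings, not tabulated AEs.

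The effect is confined to the descriptive safety tables. No efficacy result changes.

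**What to change.** - **Protocol 8.1.1:** reconcile it with 8.4.1 and 8.4.6. Record abnormalities on the Visit 1 scan as baseline findings or medical history. Record a Visit 4 CT finding as an AE only if it is new or worse than on the Visit 1 scan and not exempt under 8.4.6.
- **SAP 3.6.2.1:** state that findings from the pre-dose Visit 1 scan are not treatment-emergent, whatever time is imputed.
- **SAP 3.6.2.2:** align the exclusions with that rule, so that a baseline finding is handled in the same way whether it later clears or persists.

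The cost is a few sentences across the two documents and an eCRF completion note. The small downside is that a few findings move from the AE form to medical history.
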